Clinical End Points: The primary endpoint for this pilot study is the contracture of scar (skin grafted) surface area at 90 days post-grafting. A significant reduction in secondary graft contraction in the treatment group compared to the control group would prompt the design of a multi-center confirmatory trial. Secondary endpoints include scar roughness, biomechanics as measured by stiffness and elasticity, redness measured by erythema each examined at 90 days post-grafting and VSS/POSAS scores along with patient reported satisfaction. Additional secondary endpoints will include the examination of each measurement at mentioned above at 1 year post-grafting to examine longer term healing.

Patient Eligibility: Eligible patients are non-emergent, patients with full-thickness burns who were seen at Wake Forest Baptist Medical Center and are scheduled for treatment with autografts for burn injury. Inclusions criteria: ages 18- 89, autograft site of at least 100cm² (not involving the head, neck, hands, buttocks or perineum). All non-burn diagnosis (i.e. chronic wound, Steven-Johnsons/TEN, etc.) prisoners, pregnant women, and patients younger than 18 years will be excluded.

Patient Identification: To screen for eligible patients, the operating room schedules and surgeons' calendars will be reviewed by the clinical research coordinator (CRC), and the three burn surgeons will aid in identifying any potentially eligible adult (age 18-89) patient who is to undergo skin grafting of a full-thickness burn. After identification, study team personnel will then screen the patient for eligibility, by review of clinical information.

Patient Recruitment: Once eligible patients are identified, a qualified research team member will approach the patient and offer the opportunity to learn more about participation in this study. If the patient is willing, then the qualified research team member will proceed to complete the informed consent and enrollment process. This will be completed at the conclusion of clinical care, to avoid any duress from the pain of wounds left open to the air. In the clinic, the process will be conducted in the patient's exam room. Similarly, inpatients will also be consented in the quiet of their hospital room so as to allow them time to carefully consider the details of the study and ask questions.

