Patient Sample Size and Rationale: As this is a pilot study in humans, we used preclinical data from our porcine burn model to inform the choice of sample size. For a full clinical study we estimate a need to enroll 29 patients. We acknowledge we may not have a large enough sample size to measure significant improvement. However, the data obtained will aide in the more accurate calculation of the needed sample size for further human studies. In addition, the prospective documentation of safety will increase our competitiveness for funding for a full study. For this pilot study we propose enrolling only 15 patients - the number at which we would have conducted an interim analysis and assess safety if we were to proceed with enrollment of 29 patient s (current estimate for full study). The primary endpoint that we will assess is the scar area at 90 days post-grafting. We will conduct analysis for efficacy after the patients have each reached 90 days post-grafting using the spending function of Lan and Demets²⁴. There is not an accepted standard for the measure of graft loss or an expected "percent take". Some have proposed to use less than or greater than 50% of graft loss reflecting the difficulty²⁵. In an effort to proceed in a conservative fashion, an adverse safety outcome (namely graft loss not evident by physical changes visible on Day 7-10 photographs, will be defined as a 5% or greater, laser-associated graft loss with a rate in patients of 15% or greater deemed unacceptable. In a previous study of burn patients with heterogeneous types of scars, it was noted that those treated with FxCO₂ were most likely to complain of postoperative pain (8/42 patients, or 19%), followed by reports of fever (2 out of 42 patients, or 4.8%), development of hypopigmentation (2/42 or 4.8%), rash (1/42, or 2.4%), or blistering $(1/42, \text{ or } 2.4\%)^{26}$.

Statistical Plan and Data Analysis

The primary endpoint of the full trial is the burn scar area at 90 days post-grafting. For the primary analysis, we will compare the log transformed area of the scar for the treatment wounds to the control wounds. We will use linear mixed effects models that will adjust for fixed effects of the baseline wound surface area grafted (prior to the occurrence of any significant contracture) and treatment center. A random effect will be

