included in the model for each patient to account for dependence between the treatment and control sites. The primary analysis will follow intention to treat principles and will be conducted at the two-sided 0.05 level^{27,28}.

Secondary objective endpoints include scar roughness, biomechanics as measured by stiffness and elasticity, redness measured by erythema each, examined at 90 days post-grafting. Secondary analyses will follow the same general framework as outlined for the primary analysis. Outcome variables may be log transformed to satisfy necessary distributional assumptions for the analysis. Secondary subjective endpoints are the VSS and POSAS scores at 90 days post-grafting. These endpoints will be analyzed within the same framework as described for the other primary and secondary endpoints. In addition, we will examine all endpoints at 1 year post-grafting to characterize the effects of treatment on longer term healing.

We will also conduct exploratory longitudinal analyses of the primary and secondary endpoints. Since we will observe each endpoint at multiple visits across time, we will use longitudinal mixed effects models to explore the healing profile across time for both the treatment and control group.

For efficacy, analysis will be interested in assessing the primary endpoint through the error spending function approach described by Lan and Demets^{24,29}. For safety, an adverse safety outcome will be defined as a 5% or greater, laser-associated graft loss with a rate in patients of 15% or greater deemed unacceptable. If there are 6 adverse safety outcomes within the first 15 patients, we will terminate the study due to an unacceptable safety risk to patients.

Data Collection

Data will be collected on Case Report Forms (CRF) and individual SD cards (for photographs) kept with the CRF for each individual patient. These CRFs and SD cards will be stored in the locked office of the CRC and in a locked file cabinet.

Data and Safety Monitoring Committee

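### Does the Lan-DeMets spending function attached to the pilot's single 90-day efficacy analysis of 15 patients change its significance level?

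*Combined protocol and SAP*

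**What the plan says.** Patient Sample Size and Rationale estimates 29 patients for a full study and then limits this one: "For this pilot study we propose enrolling only 15 patients". It describes 15 as "the number at which we would have conducted an interim analysis and assess safety if we were to proceed" to 29. The same section gives the timing and method of the efficacy analysis: "We will conduct analysis for efficacy after the patients have each reached 90 days post-grafting using the spending function of Lan and Demets".

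Statistical Plan and Data Analysis opens with wording for a larger study: "The primary endpoint of the full trial is the burn scar area at 90 days post-grafting". The mixed model is to "adjust for fixed effects of the baseline wound surface area grafted (prior to the occurrence of any significant contracture) and treatment center", although eligible patients are those "who were seen at Wake Forest Baptist Medical Center and are scheduled for treatment with autografts for burn injury", which is one center. The primary analysis "will be conducted at the two-sided 0.05 level". Later in the section the efficacy work is described as "assessing the primary endpoint through the error spending function approach described by Lan and Demets".

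Clinical End Points says that a significant reduction in contraction would lead to the design of a multi-center confirmatory trial. None of these sections names a spending function, an information fraction, a boundary or a second analysis of the 90-day endpoint. The 1-year analyses concern a different time point and are secondary.

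**The concern.** A spending function divides alpha among repeated looks at the same endpoint. The plan describes one look, so the provision has nothing to divide. It sits beside a flat 0.05, in a section that still speaks of the full trial and adjusts for center in a study that recruits at one. It therefore appears to have been carried over from the 29-patient design.

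The worry is that an analyst takes it literally, treats 15 patients as the interim look of 29, and applies a boundary stricter than 0.05. Alpha would then be held back for a look at 29 patients that this study does not contain. A result with p = 0.04 would count as significant to one analyst and not to another, and significance is what would prompt the confirmatory trial.

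**Working it through.** **Inputs.** Two-sided alpha 0.05 (Statistical Plan); 15 patients in the pilot, 29 in the hypothetical full study, and one efficacy analysis once patients have reached day 90 (Patient Sample Size and Rationale). The spending form is not stated, so the common ones are all tried. The documents give no effect size, SD or power, so 29 cannot be reproduced.

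**Reproducing the stated level.** For the pilot as described, t = 15/15 = 1.

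- Pocock type: 0.05 × ln(1 + (e − 1) × 1) = 0.05
- Linear, or power family with any exponent: 0.05 × 1 = 0.05
- O'Brien-Fleming type, alpha in one piece: 2[1 − Φ(1.960/√1)] = 0.05
- O'Brien-Fleming type, 0.025 per tail: 4[1 − Φ(z₀.₉₈₇₅/√1)] = 0.05

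All forms return 0.05, as they must when all the information is in. The stated level is reproduced whichever function is meant.

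**The other reading.** Here t = 15/29 = 0.5172 (assumed; √t = 0.719).

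| Form | Calculation | Two-sided level | Critical \|t\|, 14 df |
|---|---|---|---|
| Single analysis at 0.05 | – | 0.05 | 2.145 |
| Pocock type | 0.05 × ln(1 + 1.718 × 0.5172) | 0.0318 | 2.385 |
| Linear | 0.05 × 0.5172 | 0.0259 | 2.492 |
| Power, exponent 2 | 0.05 × 0.5172² | 0.0134 | 2.830 |
| Power, exponent 3 | 0.05 × 0.5172³ | 0.0069 | 3.162 |
| O'Brien-Fleming type, one piece | 2[1 − Φ(1.960/0.719)] | 0.0064 | 3.200 |
| O'Brien-Fleming type, per tail | 4[1 − Φ(z₀.₉₈₇₅/0.719)] | 0.0037 | 3.483 |

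The 14 df treat the comparison as a paired t-test on 15 patients. A p-value of 0.04 is |t| = 2.264, which passes at 0.05 and misses every other row.

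The largest power loss against 0.05, taken over all possible effect sizes (paired t, n = 15), is 8.6 points for the Pocock type and 35.6 or 43.8 points for the two O'Brien-Fleming variants. These are upper bounds, not expected losses.

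**Which reading the text supports.** The pilot enrols only 15. The interim role of 15 is stated conditionally. A positive result leads to designing another trial, not to continuing this one, and the pilot data are to be used to recalculate a later sample size. Together these give t = 1.

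**Consistency.** If the statistical section is read as the full trial's, its 0.05 is that trial's overall level. A lower level at 15 patients then agrees with it, because the remaining alpha belongs to the look at 29. For example, the nominal final level would be 0.0273 for the Pocock type and 0.0475 or 0.0488 for the O'Brien-Fleming variants. A contradiction appears only when the full trial's boundary is combined with the pilot's single-look alpha.

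**The case for a change.** The strongest case for a change is that a prespecified plan should fix its threshold before data are seen, and this one names a procedure that cannot be run without details it omits. Some wording does favour the interim reading: the statistical section refers to the full trial, and the safety stopping rule counts events among the first 15 patients, as if more might follow. The monitoring committee meets every 6 months, and its section does not restrict it to safety data. If 90-day area were tested at an unadjusted 0.05 at one or two earlier, equally spaced looks, the overall error would be about 8.3% or 10.7%.

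It stands that the spending text is incomplete and that its role in a 15-patient pilot is not explained. The rest does not carry the point to a change. No section schedules an efficacy test at a committee meeting, so the 8.3% and 10.7% describe a different plan; and if such looks did occur, the spending provision would be useful, which argues against deleting it. The same is true if these 15 patients were later counted toward 29. The safety-rule wording makes the interim reading possible, but it does not outweigh the explicit enrolment limit and the conditional phrasing.

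**Conclusion.** The concern is accurate as a description of the text but leads to no change. With one analysis at full information the level is the stated two-sided 0.05 and the loss is zero, whichever spending function the sponsor had in mind. Levels of 0.0037 to 0.0318 arise only by assuming both a fraction of 15/29 and a spending form, neither of which the documents give. Even then the test is conservative: type I error stays at or below 0.05.

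The consequence of a stricter threshold is also small here. The proposed pilot study is presented as being conducted to establish safety, the sample-size section accepts that 15 patients may be too few for significance, and nothing says that a non-significant result blocks a later trial. Removing the spending sentences would alter no result on the better-supported reading, and would take away a safeguard on the other.

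This conclusion assumes that no efficacy test of 90-day area is made before all patients reach day 90, which is what the plan describes.

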Mean + stdev Variable p-value Insurance Burn Fund 37.4 ± 13.6 45.0 ± 19.9 0.152 Age % TBSA 9.0 + 12.0 12.3 + 13.5 0.189 % Partial Thickness Wound 5.4 + 9.4 6.7 + 8.5 0 293 % Full 3.5 + 5.8 5.3 + 6.7 0.100 Weeks between date of injury 10.5 + 9.7 7.6 + 5.4 0.089 and date garment ordered Weeks between garment 8.4 + 4.0 8.7 + 4.2 0.771 ordering and delivery Total number of weeks between 18.5 + 11.1 16.3 + 6.3 0.815 injury and garment application

Table 1. A quality improvement project was translatedinto an IRB-approved review of the time required forpatients to successfully don custom-made compressiongarments. A surprising delay was noted.

Relevance to Proposed Clinical Trial

The noted delay was, and is, concerning from a clinical care perspective. However, the clinicians have been unable to change the delays, as the process appears to have multiple logistical delays (therapist availability to measure, delays in ordering, delays in insurance approval, delays in fitting, delays in altering, and delays created by difficulty in contacting patient). These challenges notwithstanding, a unique opportunity has been created by the inability to offer a timely standard of care. The delay offers an acceptable and ethical justification to apply early laser treatment to patients – either as part of clinical care or a prospective study.

Figure 6. Skin grafts (meshed 1:1) on nearly entire dorsum of bilateral hands one day after fractional CO_2 laser treatment. No subsequent loss of graft. Displayed flexion of digits at patient maximal effort.

Limited Early Laser Treatment is Clinically Free of Complication

Due to our inability to offer a timely and effective therapy to mitigate scar formation, our surgical team at the Ohio State University has treated skin grafts with FxCO₂ during the period of initial hospital admission, when patients were returning to the OR for other procedures. This has been offered as empiric therapy and not part of

any type of study (**Fig. 6**). With recognition of those limitations, the treatment is well tolerated, with no clinical evidence of graft injury (**Fig. 6**). Also, there is anecdotal appreciation of efficacy (**Fig. 6** and **Fig 7**). We have applied the FxCO2 laser successfully in four patients. We have seen no areas of unanticipated graft damage or loss related to its use.

Relevance to Proposed Clinical Trial

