Safety is an essential concern of any proposed clinical trial. Although the experience of treating skin grafts at 6-10 days after surgery is limited at our Burn Center, it is promising. Establishing safety with an appropriately monitored study is an important unmet need. However, the preliminary data and qualitative observations are supportive that the study can be done safely.

Fig**ure 7.** At time of presentation for third planned laser treatment (not yet wearing compression garments). Note composite fists in A.

PROPOSED PILOT STUDY.

This pilot study is being conducted to establish safety, however we will make multiple measures to measures of efficacy as well. We hypothesize that human split-thickness skin grafts will safely respond similar to the porcine model when treated with the $FxCO_2$ laser and have significantly less secondary contracture than control sites.

Overall Strategy

The great majority of laser studies have addressed treatment of established scars. Ideally, treatment modalities could be moved into the acute period of injury, to shorten the recovery time of thermal burns by decreasing the

time to maximum recovery, and mitigate scar formation. The current study will address the impact on treatment of skin grafts applied in the treatment of acute burn wounds. Preliminary work completed by our team has confirmed that the red Duroc porcine model is a good model of hypertrophic scar formation in humans, and early use of the FxCO₂ on split-thickness skin grafts decreased secondary contracture. Further, we have identified a period of 19 weeks between the time custom-made compression garments are ordered and actually applied with benefit to the patient. We have identified a "therapeutic donut hole" in which we have no efficacious alternative to offer until about 19 weeks. In these patients who had larger burn returning to the OR for additional procedures, we were able to offer FxCO₂ treatment as a "salvage" therapy. With this, we have demonstrated safety for the skin graft and anecdotal efficacy. We propose a pilot study to prospectively demonstrate safety in a controlled study and attempt to establish efficacy of early (post grafting day 6-10) FxCO₂ laser treatment of split-thickness skin graft applied in the treatment of burn injuries.

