A Data Safety and Monitoring Committee (DSMC) will be formed and will meet every 6 months throughout the period during which patients are being recruited and experiencing follow-up. The DSMC will review data provided by the primary study statisticians and other study staff involved in data management and analysis. The committee will consist of [name](a trauma surgeon at WFBMC, [name], PhamD (Specialty Practice Pharmacist – Critical Care at the Ohio State University), and [name] PA (PA at the Ohio State University - experienced with appearance of grafts, laser patient care, and clinical trials. All unexpected non-serious adverse events and serious adverse events relating to participation in the study will be reported verbally and in writing to the local IRB and the study PI.. The verbal report will occur within 48 hours of the occurrence. The written report of a serious adverse event (e.g., death or life-threatening adverse event) will be reported within 7 days.

- 4. Gauffin E, Öster C, Gerdin B, Ekselius L. Prevalence and prediction of prolonged pruritus after severe burns. *J Burn Care Res.* 2015;36(3):405-413.

- 7. Simman R. Wound closure and the reconstructive ladder in plastic surgery. *J Am Col Certif Wound Spec.* 2009;1(1):6-11.

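### Below the 6-of-15 termination rule, graft-loss events have no prompt route to the DSMC and trigger no review

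*Combined protocol and SAP*

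**What the plan says.** The Statistical Plan and Data Analysis section sets the limit as a 5% or greater "laser-associated graft loss with a rate in patients of 15% or greater deemed unacceptable". The action follows at once: "If there are 6 adverse safety outcomes within the first 15 patients, we will terminate the study". Patient Sample Size and Rationale gives the same 5% and 15% figures, with a qualifier that the statistical section does not repeat: the loss must not already be visible on the day 7-10 photographs. It also fixes enrolment at 15, so the rule covers the whole pilot. Neither section gives an action for fewer than six events.

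Under Data and Safety Monitoring Committee, the DSMC "will meet every 6 months throughout the period during which patients are being recruited" and followed up. On expedited reporting, "All unexpected non-serious adverse events and serious adverse events relating to participation in the study will be reported verbally" and in writing; the recipients are the local IRB and the study PI, and the verbal report is due within 48 hours. The DSMC is not named as a recipient, and no unscheduled meeting is provided for.

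On purpose, the Proposed Pilot Study section opens: "This pilot study is being conducted to establish safety". The section before it says: "Establishing safety with an appropriately monitored study is an important unmet need". The human experience described is four patients treated outside any study, of whom the plan says: "We have seen no areas of unanticipated graft damage or loss related to its use".

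**The concern.** The unacceptable rate is 15%, but the only count that obliges anyone to act is 6 of 15, an observed 40%. Counts of three, four and five are observed rates of 20%, 26.7% and 33.3%. All lie above the plan's limit, and none has an action attached.

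The other safeguards may not fill the gap in time. A committee that meets every six months may see a cluster of losses only after further patients have been treated. The 48-hour reports go to others. They cover events that are serious or, if not serious, unexpected, and the plan does not say whether a 5% graft loss, which it names in advance as a safety outcome, is unexpected. In a 15-patient study run to establish safety, a true rate well above the limit could pass through the whole trial without the independent committee being asked to look.

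**Working it through.** **Inputs from the plan.** n = 15 patients; termination at 6 events; limit p0 = 15% of patients. No error rate is given for the safety rule; the two-sided 0.05 level is stated for the primary efficacy analysis only.

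**Assumptions.** Patients are independent with a common event probability p, and all 15 are evaluable. The true rates are illustrative, since the documents give no estimate.

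**Step 1: reproduce the boundary.** With X ~ Binomial(15, p), P(X ≥ r) = Σ from k = r to 15 of C(15,k) p^k (1−p)^(15−k). At p = 0.15:

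- P(X ≥ 3) = 0.396
- P(X ≥ 4) = 0.177
- P(X ≥ 5) = 0.062
- P(X ≥ 6) = 0.017

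Six is the smallest count with a tail at or below 0.05, and also at or below 0.025. The exact two-sided 95% lower limit is 11.8% for 5/15 and 16.3% for 6/15, so six is the first count whose interval excludes 15%. The boundary is therefore reproducible as a test against 15%. The expected count at a true 15% is 15 × 0.15 = 2.25, so three is the first whole count above it.

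**Step 2: what the rule does, and what a review trigger would add.** The column for 3 to 5 events is P(X ≥ 3) − P(X ≥ 6).

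| True rate | P(stop), X ≥ 6 | P(3 to 5 events) | P(review), X ≥ 3 | P(review), X ≥ 4 |
|---|---|---|---|---|
| 5% | 0.01% | 3.6% | 3.6% | 0.5% |
| 10% | 0.2% | 18.2% | 18.4% | 5.6% |
| 15% | 1.7% | 37.9% | 39.6% | 17.7% |
| 20% | 6.1% | 54.1% | 60.2% | 35.2% |
| 25% | 14.8% | 61.6% | 76.4% | 53.9% |
| 30% | 27.8% | 59.5% | 87.3% | 70.3% |
| 40% | 59.7% | 37.6% | 97.3% | 90.9% |

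Across true rates of 15% to 30%, 3 to 5 events occur in 38% to 62% of trials.

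**Step 3: timing.** Termination can spare a patient only if the sixth event is known before patient 15 is treated. All 15 are treated when the first 14 patients yield at most five events. Even if each outcome is known before the next patient is treated, that probability is 95.6% at a true 20%, 88.8% at 25% and 78.1% at 30%. A third event would arise among the first 14 patients, in time for a review to matter to patient 15, with probability 55.2%, 71.9% and 83.9% at the same rates.

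**Step 4: what the four earlier patients show.** For 0 of 4, the one-sided 95% upper limit is 1 − 0.05^(1/4) = 52.7%. A true rate of 30% would give 0 of 4 with probability 0.7^4 = 24.0%. So the earlier experience neither excludes the higher rates in the table nor supports them.

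**The case against.** **The stopping number is sound.** A reader might infer that 6 of 15 is a mistake because it is 40% against a 15% limit. It is not: it is what an exact test at 0.05 gives. The plan does not state that basis, but this is a missing sentence of rationale and not a fault in the rule.

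**There is monitoring below six.** A reader might infer that nothing protects patients until the sixth event. The documents do not support that. The DSMC meets during recruitment and follow-up, the IRB and the PI receive 48-hour reports, and either the PI or the DSMC could act at discretion. The qualifier in the sample size section also counts for the plan: loss that was not visible on the day 7-10 photographs and is attributed to the laser can reasonably be called unexpected and related, and so reportable. The text is not explicit, however, and on either reading the DSMC is not a recipient. The gap is one of speed, route and trigger.

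**Three to five events prove little.** A reader might infer that these counts show a rate above 15%. One-sided P values of 0.396, 0.177 and 0.062 do not show that. They justify a review, not termination.

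**The event may be small.** The plan chose 5% as a conservative threshold and notes that some have proposed 50%. With the minimum 100 cm² graft split roughly in half, and the laser site as denominator (an assumption), 5% is about 0.05 × 50 = 2.5 cm². Asking for strong evidence before termination is reasonable for such an event. This supports keeping six and does not argue against telling the DSMC.

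**High true rates are hypothetical.** No document suggests 30%, and the plan reports that laser treatment did not slow healing in the porcine model. That is fair, and the conclusion does not depend on 30%: at 20%, the rule stops 6.1% of trials while 3 to 5 events occur in 54.1%.

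**An automatic pause has a real cost.** Laser treatment is tied to days 6-10 after grafting, so patients already grafted could permanently miss the window, and holding repeat sessions could alter treatment before the 90-day endpoint. This stands, and it is why the remedy is a review and not a mandatory hold. Choosing three over four is a judgement.

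**Conclusion.** The concern holds as a gap in monitoring. The termination rule is valid but insensitive: 1.7% at a true 15%, 6.1% at 20%, 14.8% at 25%, 27.8% at 30% and 59.7% at 40%. Between it and the routine safeguards, no event-triggered DSMC review is set, although counts of 3 to 5 are common at true rates from 15% upward. For a pilot whose stated purpose is safety, this should be fixed. It does not make the design invalid.

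The probabilities rest on independent patients with a common event rate, all 15 evaluable. The timing figures also assume that each outcome is known before the next patient is treated; slower ascertainment would make both the stop and the review less protective.

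**What to change.** Keep termination at 6 of 15, and make two additions:

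1. **Data and Safety Monitoring Committee section.** Report every qualifying laser-associated graft loss of 5% or more to the DSMC within the existing 48 hours, whether or not it is judged unexpected or serious, with a running count of events and patients treated.
2. **Statistical Plan and Data Analysis section.** Convene an ad hoc DSMC review at the third such event. Leave it to the DSMC whether to continue, modify, hold or stop treatment, so that patients already grafted do not miss the day 6-10 window automatically.

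The cost is some protocol wording and a short DSMC note, with no extra patients. The downside is an unneeded ad hoc review in 3.6% of trials at a true 5% and in 18.4% at a true 10%. A trigger of four would cut these to 0.5% and 5.6%, but would reach review in 70.3% instead of 87.3% of trials at a true 30%. Three is preferred because an unneeded review costs little when it carries no automatic hold.
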